5.6.3. Missed Clinic Visits/Lost to Follow-up

[figure not shown]
The following actions must be taken in relation to a subject who fails to attend the clinic for a required study visit:

- The site must attempt to contact the subject and re-schedule the missed visit as soon as possible
- The site must counsel the subject on the importance of maintaining the assigned visit schedule and ascertain whether or not the subject wishes to and/or should continue in the study
- In cases where the subject is deemed 'lost to follow up', the investigator or designee must make every effort to regain contact with the subject (where possible, 3 telephone calls and if necessary a certified letter to the subject's last known mailing address or local equivalent methods). These contact attempts should be documented in the subject's medical record
- Should the subject continue to be unreachable, only then will he/she be considered to have withdrawn from the study with a primary reason of "Lost to Follow-up"

5.6.4. Liver Chemistry Stopping Criteria

Liver chemistry stopping and increased monitoring criteria have been designed to assure subject safety and evaluate liver event etiology (in alignment with the FDA premarketing clinical liver safety guidance). Drug-Induced Liver Injury Guidance

Phase II Liver Chemistry Stopping and Increased Monitoring Algorithm

Liver Safety Required Actions and Follow up Assessments Section can be found in Section 12.2 Appendix 2.

5.6.4.1. Study Treatment Restart or Rechallenge

Study treatment restart or rechallenge after liver chemistry stopping criteria are met by any subject participating in this study is not allowed.

5.7. Early Withdrawal

If a subject is withdrawn from the study, for any reason, they will be considered to be an Early Withdrawal. The reason for the early withdrawal will be recorded in the eCRF. The Early Withdrawal assessments, as detailed in Section 7.1 Time and Events Table, should be performed as soon as possible following withdrawal. Subjects should also attend a Follow-up visit according to the timing and assessments in Section 7.1 Time and Events Table.

5.8. Subject and Study Completion

A completed subject is one who has completed all phases of the study including the Follow-up visit.

The end of the study is defined as the last subject's last visit (LSLV).

6. STUDY TREATMENT

6.1. Investigational Product and Other Study Treatment

The term 'study treatment' is used throughout the protocol to describe any combination of products received by the subject as per the protocol design. Study treatment may therefore refer to the individual study treatments or the combination of those study treatments.

	Study Treatment				
Product name:	GSK1278863	Placebo			
Dosage form:	Tablet	Tablet			
Unit dose	5 mg and 25 mg tablet	0 mg			
strength(s)/Dosage	strengths/10 mg, 15 mg, 25 mg,	_			
level(s):	30 mg dosage levels				
Route of Administration:	Oral	Oral			
Physical description:	A round, biconvex, 10 mm white	A round, biconvex, 10 mm white film			
	film coated tablet.	coated tablet.			

All eligible subjects will discontinue their current ESA therapy and will be randomized to receive either GSK1278863 or matching placebo on a dialysis day. This should be timed such that randomization (Day 1) occurs on the date that would have been the next scheduled dose of ESA (or as close as practicable). In addition, for subjects with a three times weekly dialysis schedule, Day 1 must not occur on the first dialysis session of the week (e.g., if Monday-Wednesday-Friday schedule, the study visit cannot be on Monday). For subjects with a four to five times weekly dialysis schedule, Day 1 can be on any hemodialysis session of the week. Examples of switching are provided in the SRM.

To maintain the blind, subjects will have study treatment dispensed from three bottles of study medication. This combination of tablets will provide the appropriate dose of study medication, and will include a combination of tablet strengths, active and placebo, to correspond to the appropriate dose.

Subjects will be dispensed one tablet from each bottle (all subjects will take three tablets in total) and take with a glass of water on a dialysis day, and this should be prior to dialysis; however, on Day 1 it is acceptable for the subject to take study medication after dialysis. All study medication should be taken in the clinic **EXCEPT** prior to the PK day (Day 15 study visit), or on other days only if the Investigator and GSK Medical Monitor agree that it will not interfere with the study procedures or affect the subject's compliance

with the protocol. The study site must ensure that the date and time the subject took each dose of study treatment is documented.

On the PK day, subjects will be instructed to take their dose of study medication at home and arrive for clinic visit approx. 6-10 hr post-dose. Subjects may take their Day 15 dose the evening prior to the study visit to accommodate the 6-10 hr PK/PD sampling window. Additional instructions can be found in the SRM.

Subjects can take their tablets without regard to food. For all study visits, it is recommended for subjects not to eat a heavy meal before coming to the clinic in order to avoid lipemia of the blood sample collected for the analysis of transferrin, iron and TIBC.

6.2. Treatment Assignment

Subjects will be assigned to study treatment in accordance with the randomization schedule generated by Clinical Statistics, prior to the start of the study, using validated internal software.

The randomization schedule will be computer generated by PPD using the randomization system Prism. Subjects will be stratified as outlined in Section 4.1 and assigned a randomization number by IVWRS managed by PPD. Once a randomization number has been assigned, it must not be reassigned.

6.3. Blinding

This will be double-blind study, with the subject, investigator and site staff, and GSK study team all unaware of the study treatment received. The following will apply concerning unblinding:

- The investigator or treating physician may unblind a subject's treatment assignment **only in the case of an emergency** OR in the event of a serious medical condition when knowledge of the study treatment is essential for the appropriate clinical management or welfare of the subject as judged by the investigator.
- Investigators have direct access to the subject's individual study treatment.
- It is preferred (but not required) that the investigator first contacts the GSK Medical Monitor or appropriate GSK study personnel to discuss options **before** unblinding the subject's treatment assignment.
- If GSK personnel are not contacted before the unblinding, the investigator must notify GSK as soon as possible after unblinding, but without revealing the treatment assignment of the unblinded subject, unless that information is important for the safety of subjects currently in the study.
- The date and reason for the unblinding must be fully documented in the eCRF.

A subject may continue in the study if that subject's treatment assignment is unblinded.

• GSK's Global Clinical Safety and Pharmacovigilance (GCSP) staff may unblind the treatment assignment for any subject with an SAE. If the SAE requires that an expedited regulatory report be sent to one or more regulatory agencies, a copy of the report, identifying the subject's treatment assignment, may be sent to investigators in accordance with local regulations and/or GSK policy.

6.4. Packaging and Labeling

The contents of the label will be in accordance with all applicable regulatory requirements.

6.5. Preparation/Handling/Storage/Accountability

- Only subjects enrolled in the study may receive study treatment. Study medication is to be stored up to 30°C (86°F). Maintenance of a temperature log (manual or automated) is required.
- The investigator, institution, or the head of the medical institution (where applicable) is responsible for study treatment accountability, reconciliation, and record maintenance (i.e. receipt, reconciliation and final disposition records). Study treatment must be stored in a secure area under the appropriate physical conditions for the product. Access to and administration of the study treatment will be limited to the investigator and authorized site staff.
- Further guidance and information for final disposition of unused study treatment are provided in the SRM.
- Under normal conditions of handling and administration, study treatment is not expected to pose significant safety risks to site staff.
- A Material Safety Data Sheet (MSDS)/equivalent document describing occupational hazards and recommended handling precautions either will be provided to the investigator, where this is required by local laws, or is available upon request from GSK.

6.6. Compliance with Study Treatment Administration

When subjects are dosed at the site, they will receive study treatment directly from the investigator or designee. The date and time of each dose administered in the clinic, as well as the bottle number will be recorded in the source documents.

When a subject self-administers study treatment at home, compliance with GSK1278863 will be documented in a subject-completed paper diary and assessed through querying the subject during the site visit, documented in the source document and recorded into the eCRF. A record of the number of GSK1278863/placebo tablets dispensed to and taken by each subject must be maintained and reconciled with study treatment and compliance records. Treatment start and stop dates, including dates for treatment delays and/or dose reductions will also be recorded in the eCRF.

6.7. Treatment of Study Treatment Overdose

There is no specific antidote for overdose with GSK1278863. The expected manifestations of GSK1278863 overdosage include signs and symptoms associated with an excessive and/or rapid increase in Hgb concentration. In the event of a suspected overdose, it is recommended that the appropriate supportive clinical care be instituted, as dictated by the subject's clinical status. Additionally, patients should be monitored closely for cardiovascular events, increased heart rate and hematologic abnormalities.

6.8. Treatment after the End of the Study

Subjects will not receive any additional treatment from GSK after completion of the study.

The investigator is responsible for ensuring that consideration has been given to the post-study care of the subject's medical condition, whether or not GSK is providing specific post-study treatment.

6.9. Concomitant Medications and Non-Drug Therapies

Concomitant medications, including over-the-counter and supplements, taken during the study will be recorded in the eCRF. Start and stop dates will be recorded for general concomitant medications, while additional details of dose, route, and frequency will be recorded for supplemental iron. The potential for drug-drug interactions is described in Section 12.3 Appendix 3.

6.9.1. Permitted Medications and Non-Drug Therapies

Unless specified as a prohibited medication in Section 6.9.2, all concomitant prescription medications should be considered permitted provided they are not contraindicated for the individual subject concerned.

Regular multivitamins (at recommended daily allowance including for iron) and other vitamin supplements such as calcium and vitamin D are permitted at the discretion of the principal investigator or his/her designee.

GSK1278863 is a substrate of breast cancer resistance protein (BCRP). The potential for inhibitors of BCRP to increase the plasma exposure of GSK1278863 to any relevant extent is unknown. BCRP inhibitors are not excluded from safety/efficacy studies; Hemoglobin stopping criteria mitigate risk of increased pharmacology if co-administered. Co-administration of GSK1278863 with strong BCRP inhibitors [i.e., cyclosporine, HIV antivirals (atazanavir, lopinavir, ritonavir, tipranavir), lapatanib and curcumin] should be performed with caution.

6.9.2. Prohibited Medications and Non-Drug Therapies

Any herbal or dietary supplements, unless, in the opinion of the investigator (who should consult the Sponsor), the therapy will not interfere with the study, are prohibited from Screening to the Follow-up Visit.

New androgen therapy within the 12 weeks prior to Screening, at any time during the study, or changes to pre-existing androgen regimen during the study is prohibited.

Chronic use of non-steroidal anti-inflammatory drugs (NSAIDs) with the exception of low dose (≤325 mg/day) aspirin/acetylsalicylic acid is prohibited. Occasional NSAID use is permitted.

Use of any of the following prescription drugs from Day 1 until seven days after the last dose of study treatment is prohibited and will constitute a protocol violation:

- Strong inhibitors of CYP2C8 (e.g., gemfibrozil)
- Strong inducers of CYP2C8 (e.g., rifampin/rifampicin)

7. STUDY ASSESSMENTS AND PROCEDURES

Protocol waivers or exemptions are not allowed with the exception of immediate safety concerns. Therefore, adherence to the study design requirements, including those specified in the Time and Events Table (Section 7.1), are essential and required for study conduct.

Time and Events Tables are provided in Section 7.1 for the overall study and for the specific Pharmacokinetic/Pharmacodynamic assessments (Table 2).

Study visit days are based on the schedule for hemodialysis as follows:

- Three times weekly: Hgb levels may have the greatest variability around study visits at the beginning of the week; therefore, the Day 1, 15 and 29 study visit must not occur on the first dialysis session of the week (e.g., if Monday-Wednesday-Friday dialysis schedule, then the study visit cannot be on Monday).
- **Four to five times weekly:** Designated study visit can be on any hemodialysis session of the week.

To allow scheduling flexibility, study visits should occur within a window of ± 2 days, except for subjects on a three times weekly dialysis schedule for whom study visits must not be scheduled on the first dialysis session of the week. Post-randomization visits should be referenced back to the Randomization visit (Day 1). In exceptional circumstances, minor changes to visit structure may be permitted after consultation with the GSK Medical Monitor.

The following points must be noted:

- If assessments are scheduled for the same nominal time, **THEN** the assessments should occur in the following order:
 - 1. 12-lead ECG
 - 2. Vital signs

3. Blood draws

NOTE: The timing of the assessments should allow the blood draw to occur at the exact nominal time.

- The change in timing or addition of time points for any planned study assessments must be documented in a Note to File which is approved by the relevant GSK study team member and then archived in the study sponsor and site study files, but this will not constitute a protocol amendment.
- The IRB/IEC will be informed of any safety issues that require alteration of the safety monitoring scheme or amendment of the Informed Consent Form.
- No more than 500 mL of blood will be collected over the duration of the study, including any extra assessments that may be required.

7.1. **Time and Events Table**

Protocol Activity 1,2	Screening			Treatment Period				Follow-up
110.00017.0.0015	Week -4	Week -2	Day 1	Day 15	Day 29	Un-scheduled	Early Withdrawal	Day 43 ± 3 6
Informed Consent	Х							
Entry Criteria	Х		Х					
Physical, Medical History, Demography	Х							
HemoCue Hgb	X	X	X	X	X	X	Χ	
IVWRS Call	X	X	Х	X	X	X	Χ	X
Females Only: Serum Pregnancy Test 3		Х					Χ	X
Females Only: Estradiol and FSH (if required) 3		X						
ECG	X				X		Χ	
Vitals (Pre-dialysis and Post-dialysis) 4		X	Х	X	X	X	Χ	X
Clinical Chemistry		Х	X	X	X	X	Χ	X
Hematology		Х	Х	Х	X	Х	Χ	X
Folate and Vitamin B ₁₂	Х							
Ferritin, transferrin, total iron, UIBC	X		X		X		Χ	Χ
Pharmacokinetic/Pharmacodynamic Samples			X	X	X		X ⁵	
Blood draw for PGx			Х					
Adverse Events Assessment 7			X	Х	X	X	Χ	Χ
Review Concomitant Medications	X		X	X	X	X	Χ	X

- 1. All assessments should be done pre-dialysis except as noted.
- 2. Allowable time window of ± 2 days for all study visits, except the follow-up visit for which it is ± 3 days.
- 3. As detailed in Exclusion Criteria in Section 5.3.
- 4. Weight measured post-dialysis only & height measured at screening only.
- 5. Obtain samples as per the Day 29 visit in Table 2. If subject does not receive a dose of study medication at this early withdrawal visit, no post-dose PK/PD samples should be obtained.
- 6. Subjects who withdraw early from treatment should attend a follow-up visit 14 days ± 3 days after the last dose of study treatment.

 7. Serious adverse events are assessed from the time of consent as stated in Section 7.4.1.1.

 Table 2
 Pharmacokinetic/Pharmacodynamic Time and Events Table

PK/PD Sample	Day 1 (dose study med at clinic)	Day 15 (dose study med at home¹)	Day 29 (dose study med at clinic)
Plasma PK ²	Pre-dose	1st sample collected approx 6-10 hr post- dose on arrival. Additional sampling: 1, 2, and 3 h after this 1st sample	Pre-dose, 1, 2, and 3 h post dose
EPO & VEGF ²	Pre-dose	1st sample collected approx 6-10 h post- dose on arrival. Additional sampling: 1, 2, and 3 h after this 1st sample	Pre-dose and 3 h post dose
Hepcidin ³	Pre-dose	Single sample during visit	Single sample during visit

- 1. Subject to take their dose of study medication at home and arrive for clinic visit approx 6-10 h post-dose. Subjects may take their Day15 dose the evening prior to the Week 2 study visit to accommodate the 6-10 h PK/PD sampling window.
- 2. Sample to be collected within 30 minutes of planned collection time.
- 3. Sample can be pre- or post-GSK1278863 administration.

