3. OBJECTIVE(S) AND ENDPOINT(S)

[figure not shown]
	Objectives	Endpoints			
Prin	nary				
•	Characterize the dose-response relationship between GSK1278863 administered three- times weekly and Hgb at Day 29	•	Hgb change from baseline at Day 29		
Sec	ondary				
•	Characterize the pharmacodynamic (PD) effect of GSK1278863 dose regimens on	•	Maximum observed change from baseline in EPO		
	EPO, vascular endothelial growth factor (VEGF), hepcidin and red blood cells	•	Maximum observed % change from baseline in VEGF		
		•	Change from baseline in hepcidin at Day 29		
		•	Change from baseline in hematocrit, red blood cell (RBC) count, reticulocyte count and reticulocyte Hgb (CHr) at Day 29		
•	Characterize the steady-state PK of GSK1278863 and major metabolites	•	Descriptive PK summaries of GSK1278863 and major metabolites		
•	Assess the safety and tolerability of GSK1278863 with three-times weekly administration for 29 days	•	Incidence and severity of AEs and SAEs		
		•	Reasons for discontinuation of investigational product		
		•	Discontinuation for safety-related reasons, e.g., pre-specified stopping criteria or AE		
		•	Absolute values and changes from baseline over time in laboratory parameters, ECGs and vital signs		
Ехр	Exploratory				
•	Evaluate exposure-response relationships between GSK1278863 and PD endpoints	•	Further models (as appropriate) to describe the GSK1278863 exposure (PK or dose) response relationship with PD endpoints		

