7.5.1. Blood Sample Collection

Blood samples for pharmacokinetic (PK) analysis of parent GSK1278863 and metabolites (GSK2391220 [M2], GSK2531403 [M3], GSK2487818 [M4], GSK2506102 [M5], GSK2531398 [M6], and GSK2531401 [M13]) will be collected at the time points indicated in Section 7.1, Time and Events Table. The actual date and time of each blood sample collection will be recorded. The timing of PK samples may be altered and/or PK samples may be obtained at additional time points to ensure thorough PK monitoring.

For the PK/PD visits outlined in Table 2, sample times are approximate; however, it is imperative that **the actual date and time** of sampling is recorded in the eCRF.

- At the Day 1 Visit, pre-dose PK/PD samples will be obtained from all subjects. Record the date and time of the last ESA dose administered prior to PD sampling and the date and time of the GSK1278863 dose administered at this visit.
- At Day 15 Visit, post-dose PK/PD samples will be obtained. Initial PK/PD samples will be obtained from all subjects soon after arrival.
 - Record the date and time of the last two GSK1278863 doses taken prior to the Day 15 Visit (the last dose of GSK1278863 may be taken early on the day of the Day 15 Visit, or in the evening of the day before).
 - At Day 29 Visit, pre- and post-dose PK/PD samples will be obtained. Record the
 date and time of the last GSK1278863 dose taken prior to the Day 29 Visit, and
 the date and time of the dose taken at the Day 29 Visit.

Based on the time of dosing, samples may be obtained before, during, and after the hemodialysis procedure. The start date/time and stop date/time of the hemodialysis procedure at the Day 15 and 29 Visits will be recorded.

Details of PK blood sample collection (including volume to be collected), processing, storage and shipping procedures are provided in the Study Reference Manual (SRM).

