11.2. Appendix 2: Time & Events

11.2.1. Protocol Defined Time & Events

Protocol Activity ^{1,2}	Screening		Day 1	Treatment Period				Follow-up
	Week -4	Week -2		Day 15	Day 29	Un-scheduled	Early Withdrawal	Day 43 ± 3 ⁶
Informed Consent	X							
Entry Criteria	X		X					
Physical, Medical History, Demography	X							
HemoCue Hgb	X	X	X	X	X	X	X	
IVWRS Call	X	X	X	X	X	X	X	X
Females Only: Serum Pregnancy Test ³		X					X	X
Females Only: Estradiol and FSH (if required) ³		X						
ECG	X				X		X	
Vitals (Pre-dialysis and Post-dialysis) ⁴		X	X	X	X	X	X	X
Clinical Chemistry		X	X	X	X	X	X	X
Hematology		X	X	X	X	X	X	X
Folate and Vitamin B ₁₂	X							
Ferritin, transferrin, total iron, UIBC	X		X		X		X	X
Pharmacokinetic/Pharmacodynamic Samples			X	X	X		X ⁵	
Blood draw for PGx			X					
Adverse Events Assessment ⁷			X	X	X	X	X	X
Review Concomitant Medications	X		X	X	X	X	X	X

¹ All assessments should be done pre-dialysis except as noted.

² Allowable time window of ± 2 days for all study visits, except the follow-up visit for which it is ± 3 days.

³ As detailed in Inclusion Criteria in study protocol Section 5.2

⁴ Weight measured post-dialysis only & height measured at screening only.

⁵ Obtain samples as per the Day 29 visit in Table 2 of the study protocol. If subject does not receive a dose of study medication at this early withdrawal visit, no post-dose PK/PD samples should be obtained.

⁶ Subjects who withdraw early from treatment should attend a follow-up visit 14 days ± 3 days after the last dose of study treatment.

⁷ Serious adverse events are assessed from the time of consent as stated in study protocol Section 7.4.1.1

Pharmacokinetic/Pharmacodynamic Time and Events Table

PK/PD Sample	Day 1 (dose study med at clinic)	Day 15 (dose study med at home¹)	Day 29 (dose study med at clinic)
Plasma PK²	Pre-dose	1 st sample collected approx 6-10 hr post-dose on arrival. Additional sampling: 1, 2, and 3 h after this 1 st sample	Pre-dose, 1, 2, and 3 h post dose
EPO & VEGF²	Pre-dose	1 st sample collected approx 6-10 h post-dose on arrival. Additional sampling: 1, 2, and 3 h after this 1 st sample	Pre-dose and 3 h post dose
Hepcidin³	Pre-dose	Single sample during visit	Single sample during visit

¹ Subject to take their dose of study medication at home and arrive for clinic visit approx 6-10 h post-dose. Subjects may take their Day15 dose the evening prior to the Week 2 study visit to accommodate the 6-10 h PK/PD sampling window

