11.5.2. Baseline Definition & Derivations

11.5.2.1. Baseline Definitions

For Hgb the average of Hgb measured by the central lab, Quest, at Week -2 and Day 1 visits will serve as the baseline value. If an unscheduled Hgb value is taken pre-treatment then this will be slotted following the algorithm in Section 11.3.1 and Section 11.3.2.

Vital signs will be measured both pre-dialysis and post-dialysis. The baseline values for vital signs will be defined as:

Pre-dialysis baseline = vital sign value obtained pre-dialysis on Day 1

Post-dialysis baseline = vital sign value obtained post-dialysis at Week -2

Weight baseline= post-dialysis weight measured at Week -2.

Unless stated otherwise, the baseline value for all other lab parameters and ECG are defined as the last pre-treatment value observed. This is generally expected to be from the Day 1 visit (except for Folate, B12 and ECG, which are only measured at Week -4), although such values may be missing or unscheduled assessments may be performed before treatment start.

Parameter	Study Assessments Considered As Baseline			Baseline Used in Data Display
	Week -4	Week -2	Day 1 (Pre-Dose)	
Safety				
Vital Signs		X	X	See description above [1]
ECG	X			Week -4
Laboratory (clinical chemistry and hematology)		X	X	Day 1
Folate, Vitamin B12	X			Week -4
Ferritin, Transferrin, Total Iron, UIBC	X		X	Day 1
Efficacy				
Hgb		X	X	Mean (Quest) See description above
PK/PD				
PK Plasma, EPO & VEGF, Hepcidin			X	Day 1

NOTES:

- Three measurements of SBP, DBP and HR will be recorded at each study-specified visit and the mean of the replicate assessments will be used as the baseline value.

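### Day 29 hepcidin is not matched in timing to its pre-dose baseline, so the within-arm change can mix the Day 29 effect with any acute post-dose or dialysis effect

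*Protocol*

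**What the plan says.** Protocol Section 3 lists as a secondary endpoint: "Change from baseline in hepcidin at Day 29".

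**Baseline.** Protocol 7.5.1 states: "At the Day 1 Visit, pre-dose PK/PD samples will be obtained from all subjects". SAP 11.5.2.1 puts the row "PK Plasma, EPO & VEGF, Hepcidin" under the Day 1 pre-dose column.

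**Day 29.** Protocol Table 2, repeated in SAP 11.2.1, asks only for "Single sample during visit". Footnote 3 to that table adds: "Sample can be pre- or post-GSK1278863 administration". In the same table, Day 29 PK has a pre-dose sample and samples at 1, 2 and 3 h after the dose. EPO and VEGF have a pre-dose and a 3 h sample. PK, EPO and VEGF carry a 30-minute tolerance. Hepcidin carries no time at all.

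**Dialysis.** Footnote 1 to the Time and Events Table in Protocol 7.1 sets the default: "All assessments should be done pre-dialysis except as noted". Protocol 6.1 has patients "take with a glass of water on a dialysis day, and this should be prior to dialysis", with an exception that lets the Day 1 dose follow dialysis. Protocol 7.5.1 then says of PK/PD sampling: "Based on the time of dosing, samples may be obtained before, during, and after the hemodialysis procedure".

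**Analysis.** SAP 8.1.2 summarizes EPO and VEGF by visit and by sample time within visit. Hepcidin is summarized by visit only (SAP 11.14.6, Tables 2.31 and 2.32), on the log scale as percent change from baseline (SAP 11.5.2.2). No table, model or sensitivity analysis separates hepcidin values by dose timing or dialysis status.

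**The concern.** The two ends of the change score follow different timing rules. Baseline is fixed before the dose. The Day 29 value may come before the dose, some hours after it, or possibly during dialysis. The objective is to characterize the effect of the dose regimens on hepcidin, so a reader will take the Day 29 change as the effect after 29 days of treatment. If hepcidin moves acutely after a dose or during dialysis, part of the reported change is something else, and the planned tables give no way to see how much.

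The plan also describes timing that hepcidin does not have. SAP 11.3.1 speaks of EPO, hepcidin and VEGF together as collected at scheduled time points, and Protocol 9.4.3.4 promises PD summaries by planned collection time. Neither fits a sample with no planned time relative to the dose.

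**Working it through.** The plan gives no figure to reproduce. The check is a comparison of texts followed by an illustration on stated assumptions.

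**1. Position of the two samples**

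| | Relative to dose | Relative to dialysis |
|---|---|---|
| Day 1 (baseline) | Pre-dose | Pre-dialysis if footnote 1 applies. The Day 1 dose may follow dialysis, so pre-dose alone does not settle it |
| Day 29 (endpoint) | Before or after | Pre-dialysis if footnote 1 governs; possibly during or after if 7.5.1 is the noted exception |

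Footnote 3 concerns drug administration only. The dose normally precedes dialysis, so a sample can be post-dose and still pre-dialysis. Only the 7.5.1 sentence opens the way to sampling during dialysis. It covers PK/PD samples in general and does not name hepcidin. The dose mismatch is therefore plain in the text, while the dialysis mismatch is an ambiguity.

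**2. Illustrative shift within an arm**

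Assumptions, none of them from the documents: late samples (post-dose or on dialysis) are lower by a fraction d, and a share q of the arm is sampled late.

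Shift in the geometric mean change = (1 - d)^q - 1

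Added between-patient SD on the log scale = sqrt(q(1 - q)) × |ln(1 - d)|, which is 0.5 × |ln(1 - d)| at q = 0.5

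| d | Shift, q = 0.25 | Shift, q = 0.5 | Added log SD, q = 0.5 |
|---|---|---|---|
| 10% | -2.6% | -5.1% | 0.05 |
| 20% | -5.4% | -10.6% | 0.11 |
| 40% | -12.0% | -22.5% | 0.26 |

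**3. Chance imbalance between two arms**

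The protocol expects about 15 evaluable patients per arm. With q = 0.5, the 95% range for the difference in late share between two arms is

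1.96 × sqrt(2 × 0.5 × 0.5 / 15) = 1.96 × 0.183 = 0.358, or about ±36 percentage points.

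An imbalance at that limit would move an active-placebo contrast by 1 - (1 - d)^0.358, which is 3.7%, 7.7% or 16.7% for d = 10%, 20% or 40%.

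**4. Effect on interval width**

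Independent timing noise adds in quadrature. The documents give no hepcidin SD, so assume a log-scale SD s of 0.5 to 0.8. The widening factor is sqrt(1 + a²/s²), where a is the added SD.

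- d = 20%: a² = 0.112² = 0.0125, so intervals widen by about 1.0% (s = 0.8) to 2.5% (s = 0.5).
- d = 40%: a² = 0.255² = 0.065, so intervals widen by about 5% to 12%.

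**The case against.** The strongest case against is that the trial is randomized, double-blind and placebo-controlled, and placebo patients are sampled under the same rule. A clock or dialysis effect common to all arms would show in the placebo column and balance in expectation. This stands, with two limits. Placebo cannot separate a sustained drug effect from an acute post-dose one, because only the active arms have the latter. And no model-based placebo contrast is planned for hepcidin, so the reader compares arm summaries of about 15 patients.

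Next, nothing in the documents says that hepcidin changes within hours of a dose or during dialysis. This also stands: the existence, direction and size of any timing effect are unknown.

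Third, timing can be recovered. Protocol 7.5.1 requires actual sampling times, and dialysis start and stop times at Days 15 and 29. A split is therefore feasible, but none is pre-specified and it would divide small arms.

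Two stronger readings are tempting, and the documents support neither:

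- A reader might infer that footnote 3 directs sampling away from the pre-dialysis default. It does not mention dialysis, and it permits rather than requires post-dose sampling. Nor does the permission for a late Day 1 dose move the Day 1 blood draw.
- A reader might infer that mixed timing will pass for a treatment effect or hide a dose trend. A shift common to all arms would be visible in placebo. On the assumed SDs, the widening is small except in the most extreme case shown.

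**Conclusion.** The timing mismatch is real but minor. Day 1 hepcidin is pre-dose, and Day 29 hepcidin is one sample at an unspecified point in the visit. Whether it may be taken on dialysis is unclear, because footnote 1 to the visit table and Section 7.5.1 are not reconciled. The within-arm change can therefore combine the Day 29 effect with any acute post-dose or dialysis effect, and the planned summaries would not show it.

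The size cannot be determined from the documents. The -5% to -23% shifts rest on an assumed 10% to 40% drop in late samples and an assumed half of patients sampled late. With a quarter sampled late they are about -3% to -12%, and with no timing effect they are zero. The endpoint is descriptive and secondary. The primary Hgb analysis and the dose ratio do not use hepcidin.

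**What to change.** In Protocol Table 2 and SAP 11.2.1, set the Day 29 hepcidin sample to pre-dose, taken with the pre-dose PK, EPO and VEGF draw, and remove footnote 3 for Day 29. State that footnote 1 to the Time and Events Table (pre-dialysis) applies to hepcidin on both Day 1 and Day 29. Day 15 can stay as it is, since it is not the endpoint visit. Correct SAP 11.3.1 so that it no longer describes hepcidin as having scheduled time points that Table 2 does not set.

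If sampling is already complete, pre-specify before unblinding a hepcidin summary by pre-dose or post-dose and by dialysis status, using the recorded times. Section 7.5.1 names dialysis times for Days 15 and 29 only, so check first what was recorded for Day 1.

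The cost is one table cell and one footnote in each document, with no extra draw. The downside is slightly less scheduling freedom for one tube on Day 29.
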